**Phase of clinical investigation:**

Phase I

**Investigational drug(s):**

Losartan Potassium

## C. Clinical Protocol

### 1. Introduction:

#### 1.1 Background:

Muscle injuries stem from a variety of events, including direct trauma (i.e., muscle lacerations, contusions, or strains) and indirect causes (i.e., ischemia or neurological dysfunction). They account for a large number of all injuries sustained by participants in professional and recreational sports. In fact, muscle injuries constitute between 10% and 55% of all injuries sustained by athletes, depending on the type of sport. The hamstring muscle complex is the most commonly involved and mainly occurs in the sports requiring bursts of speed or rapid acceleration. Although muscles can undergo regeneration after injury, the healing process is slow and often culminates in incomplete functional recovery and fibrosis. The formation of dense scar tissue can impair muscle function and lead to muscle contracture and chronic pain and diminish the individual's ability to achieve full recovery and return to prior levels of performance. Despite the considerable medical need, there has been relatively little progress in the development of therapeutic approaches to enhance healing following muscle injury.

A growing understanding of the cellular and molecular events that commonly occur during fibrosis in various tissues, including skeletal muscle, has provided a strong foundation for the development of effective therapies to prevent fibrosis and improve tissue healing. Because TGF- $\beta$ 1 plays such a crucial role in tissue fibrosis, particularly in skeletal muscle, it warrants attention as a key target for anti-fibrotic applications. In an effort to test various methods of antagonizing the effect of TGF- $\beta$ 1, we have investigated the abilities of decorin, suramin, IFN- $\gamma$ , relaxin and an angiotensin II receptor blocker, to neutralize TGF- $\beta$ 1's effect and improve muscle healing after injury. Our preliminary animal studies have shown that blocking TGF- $\beta$ 1 can decrease fibrosis and improve muscle healing. Of the agents to block TGF- $\beta$ 1, Losartan (Merck), which is an angiotensin II receptor blocker, is particularly attractive for clinical application because it is FDA approved and has minimal side effects. Losartan has been in clinical use for over 20 years and has been associated with a reduction in fibrosis in several tissues, improved myoblast transplantation and protection against sarcopenia.

To evaluate the effects of Losartan on muscle healing and prevention of fibrosis we plan to conduct a phase 1 randomized double blind placebo-controlled trial to compare Losartan to placebo for the treatment of grade II and III hamstring injuries in athletes or military personnel, veterans or their families that have sustained a sports-related hamstring injury. We hypothesize that subjects who receive Losartan will have decreased

formation of fibrosis and a faster return to their prior level of activity and muscle function.

## 1.2 Rationale:

Developed in 1990, losartan potassium is an FDA-approved drug for the treatment of hypertension, left ventricular hypertrophy and diabetic nephropathy. Losartan and EXP3174 have been referenced in 184 studies according to PubMed (United States Library of Medicine). These reports have shown losartan is a specific blocker of the type-1 angiotensin II receptor, which regulates the expression of TGF- $\beta$ 1. Our research shows strong expression of TGF- $\beta$ 1 in injured skeletal muscle, which clearly implicates TGF- $\beta$ 1 in the fibrotic cascade that occurs after the onset of muscle disease or trauma. Indeed, the use of anti-fibrotic agents that inactivate TGF- $\beta$ 1 reduce muscle fibrosis, improves muscle healing and leads to enhanced recovery of injured muscle. Losartan potassium (MerckTM) is an FDA approved drug whose use has been associated with a reduction in fibrosis in several tissues. Furthermore, it has been used to improve myoblast transplantation and protect against sarcopenia.

Based on our promising experimental data in a murine muscle injury model, the goal of this phase 1 randomized double blind placebo-controlled clinical trial is to test the effects of Losartan on muscle healing after sports, military training or combat injuries. Muscle injury caused by vigorous physical activity occurs in the US Active Duty Army at rates 3 to 4 fold higher than the civilian population. Subject recruitment will include athletes or military personnel, veterans or their families that have sustained an acute sports-related hamstring injury. This is relevant to the injured military population, since advances in combat field medicine translates into high rates of survival and increased numbers of wounded warriors, with the majority of injuries occurring in the upper and lower extremities.

Recently, we performed a preliminary phase 1 case study involving two adult males with acute/recurrent hamstring muscle injury. In both patients, we initiated treatment with Losartan after the acute period of necrosis/degeneration and inflammation. Both patients demonstrated normal hamstring flexibility and strength recovery by 6-9 weeks after injury. To date (> 2 years after treatment) neither individual has suffered any re-injury to their hamstring muscles, which may represent the most important feature of the study. Furthermore, both individuals tolerated the Losartan with no reported side effects and remained normotensive throughout the 30 day course of treatment. Despite the limitations of making treatment decisions based on two case reports, we are encouraged by the results of these interventions.

Based on our basic science results and preliminary clinical experience, we hypothesize that subjects who receive Losartan for a short duration along with the current standard of care treatment after sustaining an acute grade II or III

hamstring muscle injury will have less formation of fibrosis and a faster return to their prior level of activity and muscle function when compared to a placebo control group who only receives the current standard of care treatment. To test this hypothesis we propose a phase 1 randomized double blind placebo-controlled clinical trial to compare the use of Losartan (50mg/day) to placebo in 20 individuals with an acute grade II or III hamstring injury between the ages of 18-35. The main goal of this study is to determine safety and tolerability and to provide pilot data to determine the magnitude of the effect and variability in the outcome of Losartan in comparison to placebo, which will allow a more accurate prediction of sample size for a future definitive clinical trial. Subjects enrolled in this study that are randomized to the active drug arm of the study will be given 50 mg of Losartan to be taken daily by mouth. This dose was chosen as it is the prescribed starting dose for the FDA-approved uses of losartan. It is also the dose prescribed for a case study of 2 patients with a severe hamstring strain that demonstrated improved muscle structure and function.

In conducting this phase 1 study, we will utilize the multidisciplinary collaboration of an experienced group of scientists, surgeons and physical therapists in a unique environment at the University of Pittsburgh and the USAISR (United States Army Institute of Surgical Research) at Brooke Army Medical Center (BAMC) San Antonio, Texas. The main outcome measures will be to (a) quantify the length and volume of fibrosis in the injured hamstring muscle, based on a baseline 3 Tesla MRI and a subsequent follow-up MRI examination 6 months post-injury and (b) prospectively follow the subjects to evaluate the amount of scarring and time to return to prior activity. Safety and tolerability will be assessed by monitoring adverse events, symptoms (dizziness, new fatigue, peripheral edema or urinary symptoms), hypotension, and laboratory measures of liver and renal function, hemoglobin and hematocrit counts and serum potassium and uric acid levels.

A 1999 study in the United Kingdom^67 examined the safety of losartan potassium post-marketing in over 14,000 patients. The results of this study indicate losartan potassium, like other angiotensin II receptor antagonists (ARBs), does not present any significant adverse events. The most commonly cited specific adverse events include dizziness, headache, malaise, nausea, lassitude, cough, diarrhea, dyspnea and impotence. A literature review conducted by Sica *et al.* found other adverse events being decreases in hemoglobin and hematocrit counts, dysgeusia and ageusia, migraines and acute psychosis, hepatic abnormalities, angioedema, increase in serum potassium, decrease in serum uric acid, and changes in renal function. As is the case with all drugs directly affecting the renin-angiotensin system, Losartan should not be taken by anyone who is pregnant or thinks they may be pregnant. The use of these drugs can cause neonatal injury, hypotension, neonatal skull hypoplasia, anuria, renal failure and death. To our knowledge losartan potassium has not been withdrawn from research or marketing in the United States or any other country.

## **2. Clinical Study Objectives:**

### **2.1 Primary objective:**

Our long term objective is to improve muscle healing by decreasing pathologic fibrosis that occurs after skeletal muscle injury limiting effective muscle regeneration. Our **overall hypothesis** is that Losartan, which is an angiotensin II receptor blocker, will improve muscle healing and function after acute hamstring injuries in athletes and military personnel.

In this **phase 1 prospective double-blind placebo-controlled randomized clinical** our objective will be to **evaluate safety and tolerability** and to **provide pilot data** to determine the magnitude of the effect and variability in the outcome of Losartan in comparison to placebo, which will allow a more accurate prediction of sample sized needed for a future definitive trial. The specific aims of the study are to:

#### **Specific Aim #1: To determine safety and tolerability of Losartan when used for treatment of an acute grade II or III hamstring strain.**

*Hypothesis 1a:* Use of Losartan will have an acceptable adverse event profile that is comparable to placebo. To test this hypothesis we will monitor adverse and serious adverse events throughout the duration of the study.

*Hypothesis 1b:* The side effect profile of Losartan will be comparable to placebo. To test this hypothesis we will monitor subject complaints, symptoms, hypotension, and laboratory values.

#### **Specific Aim #2: To determine the effect of Losartan on recovery of hamstring muscle function and structure following an acute grade II or III hamstring strain.**

*Hypothesis 1.1:* Subjects who receive Losartan will have a quicker return of normal hamstring muscle function, as evidenced by better flexibility and strength of the hamstring muscle when compared to the control group who receives the current standard of care treatment without Losartan.

*Hypothesis 1.2:* Subjects who receive Losartan will have less formation of fibrosis compared to the control group who receives the current standard of care treatment without Losartan.

#### **Specific Aim #3: To determine the effect of Losartan on time to return to prior level of function following an acute grade II or III hamstring strain.**

*Hypothesis 3:* Subjects who receive Losartan for a short duration along with the current standard of care treatment after sustaining an acute grade II or III

hamstring muscle injury will have a faster return to their prior level of sports activity when compared to the control group who receives the current standard of care treatment without Losartan.

**Specific Aim #4: To determine the effect of losartan on recurrence of injury following an acute grade II or III hamstring strain.**

*Hypothesis 4:* Subjects who receive Losartan will have a lower incidence of recurrent injury after return to their prior level of sports and military activity compared to the control group who receives the current standard of care treatment without Losartan.

### **3. Study Design:**

We will conduct a **phase 1 prospective double-blind placebo-controlled randomized clinical trial** to evaluate the safety and tolerability and to provide preliminary data related to the the magnitude and variability of the effect of Losartan, an angiotensin II receptor blocker, for the treatment of acute grade II and III hamstring strains in athletes and military personnel. Safety will be evaluated in terms of the adverse event profile and tolerability (Specific Aim 1). The effect of Losartan will be evaluated in terms of function and structure of the muscle (Specific Aim 2), time to return to sports (Specific Aim 3), and recurrence of injury (Specific Aim 4). Subjects will be followed over the course of 12 months after injury.

#### **3.1 Study design schematic**

After signed informed consent is provided, subjects will undergo screening that will include collection of baseline demographics, medical history, activity level, baseline vital signs (blood pressure and heart rate), blood tests including a chemistry panel with electrolytes and complete blood cell count (CBC), pregnancy test for women, physical examination, measurements of pain and hamstring flexibility and strength and a 3.0 Tesla MRI. After screening to confirm eligibility, subjects will be randomized to receive Losartan or placebo for four weeks. All subjects will undergo standard of care rehabilitation. During the period of active intervention, subjects will be followed weekly. Blood work will be repeated 2, 4, and 6 weeks after randomization. Pregnancy tests for females will also be repeated 2, 4, and 6 weeks after randomization. Throughout the remainder of the year-long study period, subjects will undergo follow-up testing at 6 and 12 weeks, 4, 6, 9 and 12 months. The study procedures over time are summarized in the table (**Table 1**) below.

**Table 1 – Summary of Study Procedures**

	Pre-treat	Day 0	1w	2w	3w	4w	6w	12w	4m	6m	9m	12m
Informed Consent	X											
Demographic Questionnaire	X											
Activity Level	X		X	X	X	X	X	X	X	X	X	X
Medical History	X											
Vital Signs ( standard and orthostatic blood pressure and heart rate)	X		X	X	X	X	X			X		
Physical Examination	X											
Blood Work	X			X		X	X					
Numerical Pain Rating Scale	X		X	X	X	X	X	X		X		
Hamstring flexibility	X		X	X	X	X	X			X		
Isometric hamstring strength testing	X		X	X	X	X	X			X		
Isokinetic hamstring strength testing							X			X		
3.0 Tesla MRI	X									X		
Randomization		X										
Day of 1 st Dose		X										
Medication Log Review			X	X	X	X						
Telephone follow-up									X	X	X	X
	Legend: pre-treat = pre-treatment; w = week; m = months											

**Figure 1 – Flow Chart for Study Design**

### **3.2 Allocation to treatment**

Subjects will be randomized in a 1:1 ratio to either treatment with Losartan or placebo. Both groups will otherwise undergo the same standard of care rehabilitation for treatment of an acute hamstring injury. The randomization list will be generated using a random number generator. An equal number of subjects will be allocated to each group in random block sizes of two and four. Group assignments will be placed in sequentially numbered opaque envelopes, which will be opened by the Project Coordinator at each site once the participant has agreed to participate in the study and baseline testing has been completed to confirm subject eligibility. Thus the treatment allocation will be concealed from the Project Coordinator and others responsible for recruitment. To minimize bias throughout the study, both the subject and individuals responsible for outcome measure collection/analysis will remain blinded to the group assignment.

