## **4. Subject Selection:**

Subjects will be drawn from the population of patients with an acute grade II or grade III hamstring injury that present to the UPMC Center for Sports Medicine or Athletic Training Rooms at the University of Pittsburgh or to the Brooke Army Medical Center. A total of 20 subjects will be enrolled in the study. A subject will consider to be enrolled in the study if he/she has provided informed consent for study participation.

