## **9.2        Sample size determination**

With an approved sample size of 20 patients (10 in each group), we will not have enough statistical power to detect statistically significant differences in clinical measures between the Losartan and placebo groups. Therefore the objective of this phase 1 trial is to observe trends by group and estimate effect sizes that can be used to inform power calculations in future clinical trials.

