## **9.4        Effectiveness analysis**

The distribution of baseline characteristics and important prognostic factors (age, sex, body mass index, pre-injury activity level, etc) will be summarized overall, and by treatment (versus control) group to assess the effectiveness of the randomized allocation. Continuous variables will be summarized with means and standard deviations, and medians and inter-quartile ranges. Categorical data will be summarized using frequencies and percentages. We will then graphically explore the distributions of the primary outcome variables (for normality or skewedness and potential outliers) using q-q plots and histograms before conducting any tests to compare the two groups. When appropriate, transformations will be applied to outcome measures that are not normally distributed.

We anticipate minimal loss to follow-up (<5% of patients) at the 6 month assessment and only 10-15% loss to follow-up at 12 months post-injury. The primary outcome measures (safety and tolerance, recovery of muscle structure and function, return to prior level of function) will be evaluated between 6 weeks and 6 months; therefore the only outcome that could appreciably be affected by lost to follow-up is recurrence of injury within 12 months. We will compare baseline characteristics between participants and drop-outs, obtain reasons for

study drop (to investigate the possible missing data mechanism), and will also conduct a sensitivity analysis (assigning poor scores and good scores to those persons with missing information differentially by treatment assignment) to evaluate the impact on our study results.

For outcome variables that are measured repeatedly, we will use mixed models to adjust for correlation among the observations from the same person as well as a clustering effect for each site. In these models, subject characteristics such as age, sex, and treatment group will be fixed effect predictors, and subject and site identification will be included as random effects. Depending on the type of outcome variable of interest, we will employ linear mixed models or mixed effect logistic regression. Though we do not anticipate statistically significant differences between the Losartan and placebo groups due to the small sample size, these analyses will guide us in developing future clinical trials.

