- Final clinical study report
- Decoding procedures for blinded trials
- Master randomization list
- Signed FDA Form 1572 Statements of Investigator (i.e. for Investigators responsible for the conduct of the clinical research study at external study sites).
- Financial disclosure information (i.e., for Investigators responsible for the conduct of the clinical research study at external study sites; also for all study site sub-investigators who will be involved in the administration of the study drugs and/or the evaluation of research subjects [i.e., who will contribute significantly to the study data])
- Curriculum vitae (i.e., for Investigators responsible for the conduct of the clinical research study at external study sites)
- Certificates of required training; e.g., human subject protections, Good Clinical Practice, etc. (i.e., for Investigators responsible for the conduct of the clinical research study at external study sites; also for all study site sub-investigators who will be involved in the administration of the study drugs and/or the evaluation of research subjects [i.e., who will contribute significantly to the study data])
- Listing of printed names/signatures (i.e., for Investigators responsible for the conduct of the clinical research study at external study sites; also for all study site sub-investigators who will be involved in the administration of the study drugs and/or the evaluation of research subjects [i.e., who will contribute significantly to the study data])
- Copies of initial and continuing IRB approval notifications (i.e., for each of the external study sites)
- Normal value(s)/range(s) for medical/laboratory/technical procedures or tests included in the clinical protocol (i.e., for each of the external study sites)
- Laboratory certification information (i.e., for each of the external study sites)
- Monitoring visit reports (i.e., for all external study sites)
- Copies of Sponsor-Investigator correspondence (including notifications of safety information) to Investigators responsible for the conduct of the clinical research study at external study sites

The Sponsor-Investigator will retain the specified records and reports for up to 2 years after the marketing application is approved for the investigational drug; or, if a marketing application is not submitted or approved for the investigational drug, until 2 years after investigations under the IND have been discontinued and the FDA so notified.

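### Section 3.2 describes one blocked randomisation list for two sites with no stratification by site; allocation stays unbiased, but the pilot effect sizes may lose some precision and be harder to interpret

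*Combined protocol and SAP*

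**What the plan says.** Section 3.2 gives the allocation method: "Subjects will be randomized in a 1:1 ratio to either treatment with Losartan or placebo"; "The randomization list will be generated using a random number generator"; and "An equal number of subjects will be allocated to each group in random block sizes of two and four". The assignments sit in numbered opaque envelopes, "which will be opened by the Project Coordinator at each site". No stratification factor is named. The section does not say whether each site has its own envelope series or how one series would be shared. The records list in section 11.2 has a single entry, "Master randomization list".

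There are two recruiting sites. Under section 4, eligible patients are those who "present to the UPMC Center for Sports Medicine or Athletic Training Rooms at the University of Pittsburgh or to the Brooke Army Medical Center".

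Section 9.4 anticipates clustering by site. For outcomes measured repeatedly it specifies mixed models in which "subject and site identification will be included as random effects". It does not mention site for the logistic or Cox analysis of recurrence. It names no specific model for days to return to practice, and does not say whether the MRI scar measurements, imaged at baseline and 6 months, come under the mixed models. The Fisher tests in section 9.5 do not involve site.

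Section 9.2 states the purpose: "With an approved sample size of 20 patients (10 in each group), we will not have enough statistical power", so the trial is meant to show trends and supply effect sizes for later planning.

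**The concern.** Blocks on a common list keep the overall arm totals close. They do not keep the arms balanced within a site when patients from both sites draw from the same sequence.

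The plan gives reasons why site could matter:
- One site is a civilian sports medicine centre and the other an army medical centre, with separate eligibility wording for military training (section 4.1).
- The MRI facilities differ (section 6.4.2.3).
- Each site has its own research assistant measuring flexibility and strength (section 6.4.2).
- Return to activity may mean practice or military training (section 6.4.2.1).

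If the arms differ by chance in their site mix, part of any between-site gap passes into the unadjusted arm difference. The effect-size estimate is the main efficacy product of this trial, so avoidable noise in it matters even though no power is claimed. The planned correction is weak: a random-effect variance estimated from two sites is barely identified, and it applies only to some outcomes.

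**Working it through.** **Inputs.** From the documents: 20 patients, 10 per arm (section 9.2); 1:1 allocation and random blocks of 2 and 4 (section 3.2); two sites (section 4). Assumed, because the documents do not give them: site shares of 50:50 and 70:30; block sizes 2 and 4 equally likely; a between-site outcome gap of 0.5 to 1 SD.

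**The plan's own figure.** The sample size of 20 is stated as approved. No significance level, power or effect size is given, so there is no calculation to reproduce. The statement that power is low is consistent: 10 per arm gives 43% power for a standardised difference of 0.8 at two-sided 0.05 (both assumed).

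**Step 1: one list used in order of arrival, site totals fixed (exact).** With m patients at the smaller site, the number a on losartan there is hypergeometric (20 patients, 10 on losartan, m drawn).
- m = 10, 7:3 or worse: 2 × (120² + 45² + 10² + 1) / 184,756 = 33,052 / 184,756 = 0.18.
- m = 6, 5:1 or worse: 2 × (252 × 10 + 210) / 38,760 = 5,460 / 38,760 = 0.14.

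Simulating 20,000 lists with the stated blocks gives 0.19 and 0.15. Blocking on a shared list therefore gives no protection within site.

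**Step 2: spread of the site imbalance.** The arm difference in site share is D = (2a − m)/10, with Var(a) = m × ¼ × (20 − m)/19.
- m = 10: Var(a) = 1.316, SD(D) = 2 × 1.147/10 = 0.23.
- m = 6: Var(a) = 1.105, SD(D) = 2 × 1.051/10 = 0.21.

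**Step 3: three ways the envelopes could be organised (simulation, site totals allowed to vary).**

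| Set-up | Some site unbalanced by 4 or more | SD of arm difference in site share | Totals not 10:10 |
|---|---|---|---|
| One list, order of arrival | about 10-14% | about 0.21-0.23 | about 11% |
| One list, consecutive run per site | about 0.3% | 0.09-0.10 | about 11% |
| Separate blocked list per site | 0% | about 0.06 | about 35% |

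The first row is below the 0.14-0.18 of step 1 because varying totals give odd site sizes, for which a difference of 4 or more means at least 5.

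**Step 4: effect on the standard error.** At 10 per arm the standard error of an arm difference is √(2/10) = 0.45 SD. Site imbalance adds (gap × SD of D)² to its variance.
- Order of arrival, gap 0.5 SD: √(0.2 + 0.11²) = 0.461, up 3%.
- Order of arrival, gap 1 SD: √(0.2 + 0.22²) = 0.498, up 11%.
- Consecutive runs, gap 1 SD: √(0.2 + 0.10²) = 0.458, up about 2.5%.
- Site lists, gap 1 SD: √(0.2 + 0.06²) = 0.451, up about 1%.

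**Step 5: what an unlucky draw looks like.** With 10 patients per site, a 7:3 split shifts the unadjusted arm difference by 0.7 − 0.3 = 0.4 of the site gap. A fixed site term removes the shift but multiplies the variance by 1/(1 − 0.4²) = 1.19. For 8:2 (exact chance 0.02) the figures are 0.6 and 1.56.

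**The case against.** The strongest reply is that a single shared list is an inference from a singular noun. Envelopes are opened at each site, which fits separate site series, and a master list kept in the records could contain site strata. Two cities drawing from one numbered stack in order of arrival would also be hard to run without central assignment, and none is described. If one list were cut into consecutive runs, most of the problem disappears. This stands: the 10-14% figure describes one reading of section 3.2, and the supportable complaint is that the section does not say which reading applies.

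Second, the added error is small beside the sampling error of a 20-patient trial, and the site gap is assumed. Several features reduce a gap: a common rehabilitation programme with shared training materials (section 6.4.1), 3 Tesla imaging with specified sequences and quality control (section 6.4.2.3), and flexibility and isokinetic endpoints expressed as side-to-side differences or ratios (section 9.1.1). This also stands, and it limits the point to a modest improvement. It does not remove it: section 9.4 itself expects a site effect, and MRI scar length and volume and days to return are not side-to-side contrasts.

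Third, site is already in the model. That is only partly an answer, because it covers the repeated outcomes alone and uses a two-level random effect.

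A reader might go further and infer that treatment is confounded with site, or that the comparison is biased. The documents do not support that. Randomisation is unbiased whichever way the list is organised, the imbalance arises by chance and is partial, and complete separation of arm by site is very unlikely unless one site enrols only a handful of patients.

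**Conclusion.** The point holds as a minor design improvement and a needed clarification. The plan names no stratification by site and leaves unstated how the envelopes are divided. Its only adjustment for site is one that two sites can barely support. The penalty runs from about 1% on the standard error, if site lists are already intended, to about 11% in the worst case (one list in order of arrival, a 1 SD site gap and no adjustment). These figures rest on assumed site shares and an assumed site gap. They also apply to patients as randomised: withdrawn subjects are replaced (sections 5.1.1, 8.4 and 13.1), so more than 20 may be randomised and balance among completers is not guaranteed under any scheme. It would be wrong to read this as invalid allocation, or to treat the 10-14% as the established risk of this trial.

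**What to change.** In section 3.2, state that a separate list with random blocks of two and four, and its own envelope series, is generated for each site. If that is already the intention, say so. In section 9.4, replace the site random effect with a fixed site term in the treatment comparisons where the data allow. For sparse outcomes such as recurrence and adverse events, where a site term may not be estimable, tabulate the arms by site so that any imbalance is visible.

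The cost is one sentence, a second list and one degree of freedom for site, with no extra patients or visits. Incomplete last blocks at two sites make the overall totals less exact: about 35% of lists would not end 10:10, against about 11% with one list. Most of these would be 9:11 and occasionally 8:12.
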